### Primary objectives and endpoints 3.1.1

Percentage of responders, defined as having at least "Improved" on both thighs according to the Global Aesthetic Improvement Scale (GAIS), as assessed live by the Treating Investigator, at Month 9.

### Secondary objectives and endpoints 3.1.2

- 1. Percentage of responders, defined as having at least "Improved" according to the Global Aesthetic Improvement Scale (GAIS), as assessed live by the Treating Investigator for each posterior thigh separately, at Month 1, 2, 6 and 12.
- 2. Percentage of responders, defined as having at least "Improved" according to the Global Aesthetic Improvement Scale (GAIS), as assessed by photography by the subject at Month 1, 2, 6, 9 and 12 for each posterior thigh separately.

### Safety objectives and endpoints

The safety objective is to evaluate the safety of Sculptra for the improvement in appearance of cellulite in the posterior thighs.

The safety endpoints are:

- 1. Incidence, intensity, time to onset and duration of adverse events (AEs) collected throughout the study period.
- Incidence, intensity, time to onset and number of days of pre-defined expected post-2. treatment events collected using subject diaries for 28 days from each treatment.

Doc id 43CASA2006 CSP Sculptra cellulite 🚣 GALDERMA MA-47276

Print date:

2021-08-25 16:18

### 3.2 Appropriateness of measurements

The aim of this study is to investigate the aesthetic improvement of cellulite appearance. The primary endpoint chosen is GAIS assessment by Investigator. The GAIS a widely used and accepted measure within the aesthetic filed. In utilizing GAIS, Investigators can evaluate and report clinically meaningful aesthetic improvement.

Effectiveness evaluation in dermal filler clinical studies includes a combination of clinician- and subjectreported outcomes. As these are aesthetic devices and elective procedures, the incorporation of the subject perspective is critical to a study for the benefits associated with dermal fillers.

The prospective subject and clinician play a central role in determining what aesthetic treatment is right, especially when there are many alternatives.

### 3.3 Clinical Hypothesis

This study has been designed to demonstrate safety and investigate effectiveness of Sculptra for the improvement in appearance of cellulite in the posterior thighs.

### 4. STUDY DESIGN

This is a prospective, early feasibility study to evaluate the safety and effectiveness of Sculptra for the improvement in appearance of cellulite in the posterior thighs.

The study will be conducted at two study centers in Canada. Approximately 30 women with intent to undergo treatment to improve appearance of cellulite will be enrolled and treated with Sculptra in three sessions spaced one month (+2 weeks) apart. Subjects will be treated at baseline, Month 1 and Month 2 including a safety follow-up phone call  $72 \pm 24$  hours after each treatment. All subjects will have a followup visits at Month 6, 9 and 12. All visits and assessments are outlined in the Schedule of Assessments in Figure 2.

### Stopping rule:

Enrollment and injections at a study center will be temporarily halted if an SAE occurs for a vascular embolic event that leads to skin necrosis, vision loss, or stroke and is determined by the Investigator to be directly or possibly related to the investigational device or injection procedure.

Effective

Print date:

2021-08-25 16:18

The SAE will be investigated by the Sponsor. If the Sponsor's investigation concludes the SAE:

- was unanticipated
- directly related to the study product or device injection procedure and
- presents an unreasonable risk to study subjects,

the study will be terminated, and the Investigators notified. The REB and RA will also be notified if the study is prematurely terminated due to safety concerns.

If the SAE does not meet the above criteria, then enrollment in the study will continue provided all other safety criteria have been met.

### 4.1 **Overall Design**

### 4.2 Study rationale and justification for design

Aesthetic treatments to correct cellulite have become an increasingly common request and have driven the growing demand for a new, effective and minimally invasive procedure. The desire for smoothening and improving the appearance of dimpled skin has traditionally been met with subcision of fibrous septa, infrared light, laser, radiofrequency, cellulite creams and massage, for example. The use of Sculptra for treatment to improve appearance of cellulite represents a minimally invasive procedure to achieve aesthetic improvement in the posterior thighs.

This study is designed to investigate the feasibility in treatment to improve clinical appearance of cellulite in the posterior thighs using Sculptra. Sculptra stimulates collagen build over time and multiple treatment sessions at least 4 weeks apart is recommended by leading experts . Based on previously performed clinical studies and post-market surveillance data, most AEs occur within two to three weeks of an injection session. In addition to the on-site follow-up visits throughout the study, at which subjects will be questioned by study center personnel about AEs, a subject diary to capture the most common injection-related events for 28 days following each treatment will be utilized in the study to facilitate reporting. The effectiveness peak may be seen up to 12 months after the initial treatment based on previous studies using Sculptra in facial areas. The 12-month duration of the study has been set to ensure the vast majority of AEs and the effectiveness peak is captured within the follow-up period.

### 4.3 Number of subjects and study centers

Approximately 30 women will be included across two study centers in Canada.

### 4.4 Study duration

The planned clinical study duration from First Subject First Visit (FSFV) to Last Subject Last Visit (LSLV) is approximately 15 months. A subject will be involved in the study for up to 13 months, including a screening phase of up to 30 days and follow-up time after last injection. End of study is when enrollment has reached the target number of subjects and all subjects have completed the last study visit.

### 4.5 Study visits description and procedures

All study visits and assessments are outlined in the Schedule of Assessments in Figure 2.

CONFIDENTIAL

QMS-9581, CSP template (medical device), version 4.0

Page 22(63)

Effective date: 2021-06-21 06:13

Print date:

2021-08-25 16:18

# GALDERMA

## 4.5.1 Visit 1, Screening (Day -30 to Day 1)

The screening visit and baseline visit (Day 1) may be performed on the same day. The following activities and screening assessments will be performed within 30 days prior to baseline.

- Obtain Informed Consent prior to conducting any study specific procedure.
- Assess eligibility: Review inclusion/exclusion criteria.
- Obtain demographic data: date of birth, height, weight, gender, ethnicity, race and Fitzpatrick Skin Type (FST).
  - FST is a skin classification system that categorizes different skin colors, and their reactions to ultraviolet light. 18 19. For determination of the FST, see Table 1 below.
  - Height may be self-reported, weight is to be measured at clinic.
- Record the subject's medical history (including any prior dermatological procedures or implants).
- Record the subject's prior and concomitant therapies.
- Perform Urine Pregnancy test for all females of childbearing potential (prior to treatment). Test result must be negative for the subject to be eligible for treatment.
- Schedule the baseline and treatment visit (Day 1) if performed on a different day than screening.

## Table 1 Fitzpatrick Skin Types (FST)

Skin type	Skin color	Skin characteristics
I	White; very fair; red or blond hair; blue	Always burns, never tans
	eyes; freckles	
II	White; fair; red or blond hair; blue, hazel or	Usually burns, tans with difficulty
	green eyes	
III	Cream white; fair with any eye or hair color;	Sometimes mild burn, gradually tans
	very common	
IV	Brown; typical Mediterranean Caucasian skin	Rarely burns, tans with ease
V	Dark brown; Middle Eastern skin types	Very rarely burns, tans very easily
VI	Black	Never burns, tans very easily

### 4.5.2 Visit 2a, Baseline and First treatment (Day 1)

The screening visit and baseline visit (Day 1) may be performed on the same day. If Screening visit and Baseline visit are not performed on the same day, the following should be repeated:

- Review for changes in concomitant therapies.
- Re-confirm eligibility criteria.
- Perform Urine Pregnancy test for all females of childbearing potential (prior to treatment). Test result must be negative for the subject to be eligible for treatment.

Once the subject is deemed eligible by the Treating Investigator, the following procedures should be completed:

CONFIDENTIAL

QMS-9581, CSP template (medical device), version 4.0

Page 23(63)

Print date:

2021-08-25 16:18

- Obtain pre-treatment Photography.
- Perform pre-treatment ultrasound.
- Assess severity of depressions and undulations associated with cellulite using the GCTS -Treating Investigator.
- o Sculptra administration.
- o CC
- o Evaluate the subject for post-treatment AEs Treating Investigator.
- o Evaluate for device deficiencies Treating Investigator.
- Dispense diary and instruct subject on daily Diary completion. Remind subject to bring the Diary to the next study center visit.
- o Evaluate the subject for device palpability Treating Investigator.
- o Inform subject about the follow-up telephone call 72-hours (±24 hrs) after the visit.
- O Schedule the next visit 1 month (+2 weeks) after baseline.

## 4.5.3 Visit 2b, Follow up 72-hour telephone call (±24 hours)

- o Interview subject regarding any concomitant therapies.
- Interview subject regarding any AEs that have occurred since receiving treatment. If AEs are reported, notify the Investigator immediately and determine whether subject should return to the study center for an unscheduled visit. The Investigator should assess all reported AEs in a timely manner.
- Interview subject regarding the diary completion and reported events since receiving treatment. Remind subject to complete the diary daily and bring it to the next on-site visit.

## 4.5.4 Visit 3a, Second treatment (1 month (+2 weeks) after Baseline

- Review for changes in concomitant therapies.
- Collect and review subject diary.
- o Obtain pre-treatment Photography (2D and 3D).
- o Assess GAIS Subject and Treating Investigator.

## CCI

- Assess severity of depressions and undulations associated with cellulite using the GCTS -Treating Investigator.
- O Assess whether optimal treatment result has been obtained (as agreed by the Treating Investigator and Subject). If a second treatment is to be performed, confirm eligibility criteria:
  - Perform Urine Pregnancy test for all females of childbearing potential (prior to treatment). Test result must be negative for the subject to be eligible for treatment
  - No treatment should be given in the subject has a disease or condition described in the exclusion criteria, or an ongoing treatment related AE that in the opinion of the Treating Investigator would be worsened by a treatment.

Doc id 43CASA2006 CSP Sculptra cellulite GALDERMA **MA-47276** 

Print date:

2021-08-25 16:18

For subjects who receive a second treatment:

- Sculptra administration.
- CCI 0
- Evaluate the subject for post-treatment AEs Treating Investigator.
- Evaluate for device deficiencies Treating Investigator. 0
- Dispense diary and instruct subject on daily Diary completion. Remind subject to bring the Diary to the next study center visit.
- Evaluate the subject for device palpability Treating Investigator.
- Inform subject about the follow-up telephone call 72-hours ( $\pm 24$  hrs) after the visit.
- Schedule the next visit 1 month (+2 weeks) after second treatment.

### 4.5.5 Visit 3b, Follow up 72-hour telephone call (±24 hours)

- Interview subject regarding any concomitant therapies.
- Interview subject regarding any AEs that have occurred since receiving treatment. If AEs are reported, notify the Investigator immediately and determine whether subject should return to the study center for an unscheduled visit. The Investigator should assess all reported AEs in a timely manner.
- Interview subject regarding the diary completion and reported events since receiving treatment. Remind subject to complete the diary daily and bring it to the next on-site visit.

### 4.5.6 Visit 4a, Third treatment (1 month (+2 weeks) after second treatment

- Review for changes in concomitant therapies.
- Collect and review subject diary.
- Obtain pre-treatment Photography (2D and 3D).
- Assess GAIS Subject and Treating Investigator.

- Assess severity of depressions and undulations associated with cellulite using the GCTS -Treating Investigator.
- Assess whether optimal treatment result has been obtained (as agreed by the Treating Investigator and Subject). If a third treatment is to be performed, confirm eligibility criteria:
  - Perform Urine Pregnancy test for all females of childbearing potential (prior to treatment). Test result must be negative for the subject to be eligible for treatment.
  - No treatment should be given in the subject has a disease or condition described in the exclusion criteria, or an ongoing treatment related AE that in the opinion of the Treating Investigator would be worsened by a treatment.

For subjects who receive a third treatment:

- Sculptra administration.

GALDERMA

Title
43CASA2006 CSP Sculptra cellulite

MA-47276

Print date:

2021-08-25 16:18

- o Evaluate the subject for post-treatment AEs Treating Investigator.
- Evaluate for device deficiencies Treating Investigator.
- Dispense diary and instruct subject on daily Diary completion. Remind subject to bring the Diary to the next study center visit.
- Evaluate the subject for device palpability Treating Investigator.
- o Inform subject about the follow-up telephone call 72-hours (±24 hrs) after the visit.
- o Schedule the next visit at Month 6 (2 weeks) after second treatment.

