### SCHEDULE OF ASSESSMENTS

## Figure 2 Schedule of Assessments

Activity	Screening	Baseline 1st Treatment	Telephone Contact	Month 1 2 nd Treatment (optional)	Telephone Contact	Month 2 3 rd Treatment (optional)	Telephone Contact	Month 6 Follow-up	Month 9 Follow-up	Month 12 Follow-up /Early termination
	Visit 1 	Visit 2a 	Visit 2b	Visit 3a⁴	Visit 3b6	Visit 4a 	Visit 4b6	Visit 5	Visit 6	Visit 7
	(≤ 30 days of Baseline)	Day 1	72 hours (±24 hrs) after 1st treatment	One month (+2 weeks) after 1st treatment	72 hours (±24 hrs) after 2 nd treatment	One month (+2 weeks) after 2 nd treatment	72 hours (±24 hrs) after 3 rd treatment	Month 6 (±2 weeks) after Baseline	Month 9 (±2 weeks) after Baseline	Month12 (±2 weeks) after Baseline
Informed consent	X									
Inclusion/Exclusion criteria	X	$X^3$								
Demographic data (date of birth, height, weight, gender, ethnicity, race and Fitzpatrick Skin Type	Х							X 	X 	X 
Medical History	X									
Prior therapies	X									
Concomitant therapies/procedures	X	X	X	X	X	X	X	X	X	X
Adverse Events (AEs)		X	X	X	X	X	X	X	X	X
Urine pregnancy test 	X	$X^3$		$X^3$		$X^3$				X
Photography, incl 3D imaging		$X^3$		$X^3$		$X^3$		X	X	X
Sculptra administration		X		$X^4$		X 				
Device deficiencies		X		X 		X 				
Dispense subject diary (injection related events)		X		X		X				
Review subject diary completion			X	X	X	X	X	X		
Collect subject diary				$X^3$		X 		$X^6$		
Device palpability		X		X		X		X	X	X
Ultrasound		$X^3$							X	X
Treating Investigator assessments										
Global Aesthetic Improvement Scale (GAIS)				$X^3$		$X^3$		X	X	X

- Screening and baseline visits may occur on the same day, if visits occur the same day assessments will not be duplicated
- 2) Females of childbearing potential
- 3) Pre treatment
- 4) If treatment is not performed this is a follow up visit
- 5) Only applicable if treatment is performed at this visit
- 6) If applicable (i.e. if treatment was performed at the previous visit)
- 7) Weight only

- 8) Immediately post treatment and 30 minutes post treatment.
- 9) For subjects that did not receive the optional treatment at Month 1, this is a follow up visit.

Note: One month is defined as 4 weeks in the study

CONFIDENTIAL

QMS-9581, CSP template (medical device), version 4.0 Page 12(63)

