## 4.5.8 Visit 5, Follow up Month 6 (±2 weeks) after Baseline

- Obtain weight.
- o Review the subject's concomitant therapies.
- o Obtain Photography (2D and 3D).
- o Evaluate the subject for AEs Treating Investigator.
- o Collect and review subject diary (only applicable for subjects who received a third treatment).
- o CCI
- o Evaluate the subject for device palpability Treating Investigator.
- o Assess GAIS Subject and Treating Investigator.

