### 4.5.9 Visit 6, Follow up Month 9 (±2 weeks) after Baseline

- Obtain weight.
- o Review the subject's concomitant therapies.
- o Obtain Photography (2D and 3D).
- o Evaluate the subject for AEs Treating Investigator.

Doc id 43CASA2006 CSP Sculptra cellulite GALDERMA **MA-47276** 

Print date:

2021-08-25 16:18

- 0
- Evaluate the subject for device palpability Treating Investigator. 0
- Assess GAIS Subject and Treating Investigator.

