5.8 Visit Windows

All endpoints will be summarized and analyzed by nominal visit as recorded on the CRF. Data collected at unscheduled visits will be listed only, with the exception of baseline data (see Section 5.5).

Study dates outside of visit windows as described in the Schedule of Assessments presented in the Study Protocol will be considered protocol deviations. Methodology for summarizing out-of-window visit durations are described in Section 6.3.1 of this SAP.

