6.3.1 Out of Window Visit Duration

When a subject performs a planned study visit outside of the protocol-specified visit windows, the subject has an out of window study visit, which is considered a type of protocol deviation for this study. Knowing a subject's Screening visit and Baseline visit and using the protocol-specified visit windowing, one can calculate a subject's target study visit window date range for each planned study visit. Then, by comparing a subject's actual study visit date to the target study visit window date range, one can calculate the days over/under the actual study visit was in relation to the target study visit date, or study visit out of window duration. The duration, in days, a study visit is out of window will be summarized overall and by visit. Duration will be split into the following below categories. Duration categories will include both days before and days after the target planned visit date.

- +/- 1-2 days
- +/-1 3-7 days
- +/- 8-20 days
- +/- 21 or more days.

The number and percentage of subjects within each out of window duration category will be presented descriptively.

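### Protocol 4.5.6 books the Month 6 visit from the second treatment, but 4.5.8 and Figure 2 count it from Baseline, so an on-target booking falls 14–28 days past the window

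*Protocol*

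**What the plan says.** Protocol 4.5.6 lists the steps at Visit 4a. Under the steps for subjects who receive a third treatment, the last one is "Schedule the next visit at Month 6 (2 weeks) after second treatment". After the 72-hour telephone call, the next visit is Visit 5.

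Two other places in the protocol fix the date of Visit 5, and both count from Baseline. The heading of 4.5.8 reads "Visit 5, Follow up Month 6 (±2 weeks) after Baseline", and the Visit 5 column of Figure 2 reads "Month 6 (±2 weeks) after Baseline". The visit after it follows the same rule: "Visit 6, Follow up Month 9 (±2 weeks) after Baseline". Figure 2 also sets the length of a month: "Note: One month is defined as 4 weeks in the study".

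SAP 5.8 takes its windows from Figure 2: "Study dates outside of visit windows as described in the Schedule of Assessments presented in the Study Protocol will be considered protocol deviations". The same section says "All endpoints will be summarized and analyzed by nominal visit as recorded on the CRF", so a late Visit 5 stays in the Month 6 summaries.

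**The concern.** The booking line uses a different starting point from the visit's own definition. It applies only to subjects treated at Visit 4a; for everyone else the only date given is the one counted from Baseline. Read literally, the protocol gives different Month 6 dates according to whether the optional third treatment was given.

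If a site follows the line, four things happen:

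- Each such Visit 5 becomes a protocol deviation, although the site did what 4.5.6 told it to do.
- The investigator and subject GAIS results at Month 6, and the GAIS graphs over time, include assessments made well after Month 6. The lateness is tied to treatment exposure, because only three-treatment subjects are seen late. Protocol 4.2 expects collagen to build over time, so timing could matter.
- On-site adverse event review, palpability assessment and collection of the third diary all move later.
- The data review in SAP 5.10, which waits for every subject's Month 6 visit, could be delayed.

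**Working it through.** The plan states no figure for this discrepancy, so there is none to reproduce. The check is day arithmetic, with all days counted from Baseline.

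Inputs:
- One month = 28 days (Figure 2 note).
- Second treatment: 1 month, +2 weeks, after Baseline (Protocol 4.5.4), so day 28 to 42. The window runs late only.
- Third treatment: 1 month, +2 weeks, after the second (Protocol 4.5.6), so day 56 to 84.
- Visit 5: Month 6 ±2 weeks from Baseline (4.5.8 and Figure 2).
- Visit 6: Month 9 ±2 weeks from Baseline (4.5.9).
- By footnote 9 of Figure 2, a subject not treated at Month 1 is not treated at Visit 4a. Everyone given a third treatment therefore had the second at Visit 3a.

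Results:
1. Visit 5 window: 6 × 28 = 168; 168 ± 14 = day 154 to 182.
2. On-target booking under 4.5.6: 28 + 168 = 196 to 42 + 168 = 210. In four-week months that is 196/28 = 7.0 to 210/28 = 7.5.
3. Past the upper limit: 196 − 182 = 14 to 210 − 182 = 28 days.
4. Past the target: 196 − 168 = 28 to 210 − 168 = 42 days.
5. If the bracketed two weeks in 4.5.6 is assumed to mean ±2 weeks, the range is 196 − 14 = 182 to 210 + 14 = 224. It meets the window only at day 182, which needs a second treatment on day 28 and a visit a full two weeks early.
6. Month 6 to Month 9 interval: 9 × 28 = 252. Planned, 252 − 168 = 84 days. Under 4.5.6, 252 − 210 = 42 to 252 − 196 = 56 days, a cut of 50% to 33%.
7. Third treatment to Visit 5: on the Figure 2 target, 168 − 84 = 84 to 168 − 56 = 112 days. Under 4.5.6, 168 − 42 = 126 to 168 − 28 = 140 days.

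Sensitivity to the month: with the 365.25/12-day month that SAP 5.6 uses for durations, the excess over the upper limit would be 30.4 + 0 − 14 = 16.4 to 30.4 + 14 − 14 = 30.4 days. The protocol's own definition rules that reading out for scheduling, and the conclusion would be the same.

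In the SAP 6.3.1 table, the category depends on the reference point, which that section leaves unclear. Measured from the window limit (14–28 days), these visits fall in the 8–20 day category or in "21 or more days". Measured from the target date (28–42 days), all fall in the latter.

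**The case against.** The strongest reply is that the documents show which date governs. Protocol 4 and 4.5 and SAP 4.1 refer the reader to Figure 2 for all visits, and SAP 5.8 takes its windows from there. The line in 4.5.6 looks like wording carried over from the end of 4.5.4, where counting from the second treatment is correct. A site that checks Figure 2 will book correctly.

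Even if a site does not, the consequences are modest. The study is a single-arm pilot of about 30 subjects. SAP 7.3 interprets the secondary results descriptively, the visit-timing exclusion from the per-protocol set concerns Month 9 only, and SAP 6.3.1 would show the late visits. The SAP 5.10 review uses uncleaned listings without a formal report. If almost everyone has three treatments, the result is closer to a uniform delay than a mixture of assessment times.

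All of this stands as a limit on weight; none of it makes the line correct. Section 4.5.6 is the step staff work from when they book Visit 5, and Protocol 10 does not allow the investigator to deviate from the protocol. A uniform delay would still put an assessment at 7 to 7.5 four-week months under a Month 6 label. The SAP 6.3.1 table reports lateness afterwards and cannot recover on-time data.

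**Conclusion.** The inconsistency is real and should be corrected, though its effect is limited. Followed on target, 4.5.6 puts Visit 5 14 to 28 days past the upper window limit. This rests on the protocol's 28-day month and on a second treatment given within its own window. It does not depend on the missing sign before the two weeks, which may have been lost when the text was extracted, because the wrong starting point is written in words.

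Any harm is conditional on a site following this line rather than Figure 2. It is confined to subjects given a third treatment and to Month 6 data. The documents do not say how many subjects that is (0 to about 30) and give no basis for estimating the effect on the Month 6 responder rate. The Month 9 primary endpoint is unaffected.

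**What to change.** Change the last step of Protocol 4.5.6 so that Visit 5 is booked at "Month 6 (±2 weeks) after Baseline", and notify both sites. An on-target booking then falls on day 168, inside the window of day 154–182. Where a Visit 5 has been booked under the present line but not yet held, rebook it within the window if there is still time.

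The cost is one phrase and a note to sites. A formal protocol amendment also needs ethics board approval under Protocol 12.1, so a site clarification could go out first. Nothing changes in the SAP, the number of visits or the data collected, because SAP 5.8 and 6.3.1 already rely on the protocol's scheduled windows.
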